3.1.2. Limitations of prior studies

Prior studies (table 1)

- Studies often included polyps of <20mm. Because of the association between size and complications, results from these studies do not reflect complications with resection of ≥20mm polyps.
- Most studies were retrospective. Complications following within a 30-day window may go unnoticed (selection bias). There are few larger studies that evaluated complications prospectively. The risk of overall complications varied between 8% and 18%, with a bleeding risk between 3% and 14%.

Proposed study

The study will only include patients with non-pedunculated ≥20mm polyps.

The design will be a prospective RCT.

- The follow-up interval was not always clear, which may also lead to underreporting of delayed complications.
- The definition of what was considered a complication was not always provided.
- The denominator of how complications were measured was not always clear. The incidence could be related to number of polyps or number of patients (a patient could have more than one polyp).

Complications will be assessed within 30 days following the procedure.

Complications will be defined as clinical events following polyp resection, which require a visit to the ED, admission, or additional tests or procedures (see outcome measures).

We will calculate the incidence of complications per polyp and per patient.

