3.1.4. Clipping and complication risk

It is apparent that resection of a large polyp leaves behind a large mucosal defect. The mucosal ulcer that forms after polyp resection can take several weeks to heal. Bleeding complication typically occur within 7 to 10 days, requiring often admission, a repeat

colonoscopy to stop bleeding, and possible blood transfusions. To reduce the risk of bleeding it has been proposed to close the mucosal defect after polyp resection.

To date, no randomized trial has examined whether clip application affects complications after large polyp resection. One recent study did not show a benefit²¹. Bleeding occurred in 2% in either group. However, the study included patients with smaller polyps (mean size 8mm) with a low expected bleeding risk. A recent retrospective study by Liaquat et al. showed that clip closure was associated with a significantly reduced risk of delayed bleeding (2% vs. 10%), and a reduced risk of overall complications (4% vs. 12%), when compared to historical controls²². Main limitations of the study include unmeasured factors that may have affected the outcome and performance of all resections by one expert colonoscopist. However, a third very recent retrospective study by Qumseya et al. reviewed their experience with 525 large colon polyp resection and did not find that clip closure was associated with delayed bleeding complications¹⁶.

In clinical practice use of clips after polyp resection is largely dependent on endoscopist preference and availability. In preparation for this study informal evaluation of polyp resection practice showed that some endoscopists use clips, and others do not. The unclear benefit with using clips, the required technical skills to achieve clip closure of the mucosal defect, and the additional cost may prevent some from using clips routinely.

Whether clip application prevents bleeding and other complications following resection of large polyps and may reduce overall cost of care remains an important clinical question: there is no established superior method, the issue arises daily, the potential impact on clinical practice from a definitive trial would be significant, both to establish an optimal approach and in terms of patient benefits.

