3.2.9.2. Study endpoints

Endpoints of primary analysis (Comparison between clip group versus no-clip group within 30 days of follow-up):

Primary endpoint:

- *Delayed bleeding complications:*

Delayed bleeding is a serious adverse event that is defined as a patient who left the endoscopy unit and subsequently had to return to any health care facility for evaluation of rectal bleeding AND who required either hospitalization, transfusion, a repeat colonoscopy or sigmoidoscopy for examination of the polypectomy site or control of bleeding, or surgery within 30 days after completion of the colonoscopy.

Secondary endpoint:

- *Complications overall:* Overall complications will be defined as an aggregate of all complications that occur at the time of the procedure (immediate complications) or during 30 days of follow-up. They include bleeding complications as defined above, perforation, postpolypectomy syndrome, and clinical events that require an ED visit, admission to the hospital, or additional testing or intervention.

Explorative:

- *Immediate and delayed complications:* Immediate complications are considered all complications at the time of polyp resection. They include bleeding that cannot be controlled by endoscopic intervention, perforation, or clinical events that require abortion of the procedure. Delayed complications are complications that occur following the completion of the colonoscopy within 30 days of the procedure.
- *Complete and partial clip closure:* Degree of closure of the resection defect will be categorized as completely closed, partially closed, and not closed. Complete closure is defined if opposing resection margins are drawn together by clips from one side to the other, with gaps of less than 1cm between the clips. A site is considered partially clipped if only a portion of the defect could be closed¹⁷.
- *Factors associated with complications:* Factors that may be associated with complications, including polyp size, location of the polyp in the colon (right, left, rectum), histology, polyp morphology, time required for resection.

Endpoints of secondary analysis (entire study cohort):

- *Complete polyp resection:* Rate of complete study polyp resection a) at the initial colonoscopy and b) at first follow-up endoscopy
- *Polyp recurrence:* Rate of recurrent polyp at the resection site after complete polyp resection.

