3.2.10. Statistical analysis

3.2.10.1. Primary analysis: Comparison between clip group vs. no-clip group, 30 day follow-up)

Primary endpoint: Delayed bleeding complication.

We will assess the null hypothesis that clipping has no effect on delayed bleeding complications using a chi-square test to compare the two study arms (as randomized, intention-to-treat), or a Fisher's exact test if appropriate with a 5% significance level.

Secondary endpoint: Overall complications.

The secondary endpoint will be compared between the clip and no-clip arms using a chi-square test (or Fisher's exact test if appropriate) with a 5% significance level.

The primary endpoint (delayed bleeding complication) and secondary endpoint (overall complications) are planned to be used to support clip-labeling plans.

The main analyses of the primary and secondary endpoints will be done on a per subject basis. Additional analysis will be conducted at the unit per polyp. Clustering of polyps within patients (estimated to occur in approximately 5%) will be accounted for by using the method generalized estimating equations as well as mixed-effects-analysis with a random intercept for patient.

Subgroup Analyses: While the study is not powered to look at subgroups we will conduct exploratory analyses to determine if any difference in the clip and no-clip arms is modified by characteristics such as time of occurrence (immediate vs. delayed) and by etiology (bleeding, perforation, etc.). This examination will be descriptive because the study will unlikely be sufficiently powered for identifying differences as significant.

Explorative analysis of the effect of electrocautery setting: The comparison between the two electrocautery settings (low power coagulation vs. Endocut) will be explorative. Pilot data show that one third of participating endoscopists typically use low power coagulation and two thirds use Endocut. Acknowledging a possible effect of cautery on the incidence of complications there is a need to standardizing the cautery setting for the EMR procedure. Rather than using one cautery setting for all procedures, the cautery setting will be standardized by randomizing patients to one or the other setting. At the same time this randomization will allow an explorative analysis of the effect of cautery on complications. This

information, although descriptive, would provide valuable guidance to develop resection standards.

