3.2.10.3. Interim Analysis

An interim analysis will be conducted when we have enrolled 50% of the targeted 1020 patients, and completed 30-day follow-up on them. We will conduct an efficacy and futility analyses. For efficacy of clipping we will stop the trial if the two-sided p-value is less than 0.01. This alpha spending means that at the final analysis, a two-sided p-value less than 0.044 will be considered significant. At the interim look we will calculate the conditional power and terminate the study for futility if the conditional power is less than 20%. If the study will be continued, we will not modify the sample size based on the results of the interim analysis.

Because higher risk lesions may be more likely to benefit from clip closure the study should not continue to enroll patients if such benefit is apparent before study completion. We will therefore perform an interim safety sub-analysis for two groups of patients:

- (a) Patients with study polyps >4cm, and
- (b) Patients who are on anticoagulation or resume anticoagulation within 14 days of the polyp resection.

We assume that either group will contribute 10 to 20% to the study. We plan to conduct this safety analysis for each of these subgroups after 60 patients have been enrolled into either of the two subgroups (i.e. after enrollment of 60 patients with a >4cm study polyp and separately after enrollment of 60 patients who resumed anticoagulation after polyp resection). For example, the safety analysis would detect the occurrence of 2 vs. 9 delayed bleeding complications in the non-clip vs. the clip group as a significant difference (RR 4.5, 95% CI 1.01, 19.96). The study should cease to enroll these patients if the interim safety analysis shows a significantly increased relative risk in delayed bleeding complications in the non-clip group compared to the clip-group (see also Section on Monitoring).

A second safety analysis for these two groups will be part of the interim analysis after enrollment of 50% of patients (see above). Similarly, should this analysis show a significant difference in delayed bleeding complications, these patients should not be further enrolled.

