3.2.10.4. Sample Size Determination

Our sample size calculation is based on the primary aim. We hypothesize that polyp resection with clip closure of the mucosal defect will reduce the incidence of delayed bleeding complications. Prior studies have reported an overall bleeding incidence between 2 and 24% (table 1). We consider an absolute difference of 5% in delayed bleeding incidence (e.g. 8% and 3%) as clinically important. Assuming a two-sided alpha of 0.05 and a power of 80%, the study will need to include a total of 730 subjects (365 subjects into each group) to show such difference as significant. We assume that for approximately 20% of patients clip

closure will not be considered possible. Therefore approximately 920 patients will need to be included. However, approximately 10% of potential study polyps of referred patients will not meet inclusion criteria (screen failures). We estimate therefore that we need to enroll (=consent) a total of 1,020 patients for 920 patients to undergo the study intervention.

Because the primary outcome measure (delayed bleeding) will be assessed after 30 days of the colonoscopy we do not expect any dropouts.

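### Overall complications is tested at 5% for clip labelling whatever the delayed-bleeding result; a stated testing order would remove a modest excess of false favourable results at almost no cost

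*Combined protocol and SAP*

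**What the plan says.** Section 3.2.10.1 compares delayed bleeding (primary) between the randomised arms by chi-square or Fisher's "exact test if appropriate with a 5% significance level". It then gives overall complications (secondary) the same choice of tests and the same 5% level, with no condition attached. The next sentence reads: "The primary endpoint (delayed bleeding complication) and secondary endpoint (overall complications) are planned to be used to support clip-labeling plans".

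Section 3.2.10.3 adjusts for the interim look at half of enrolment. The trial stops for efficacy of clipping at two-sided p<0.01; otherwise, "at the final analysis, a two-sided p-value less than 0.044 will be considered significant". The sponsor will also "terminate the study for futility if the conditional power is less than 20"%. That section does not mention overall complications, the effect assumed for conditional power, or whether the futility stop is binding.

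Section 3.2.9.2 makes overall complications a wider composite that contains the primary: "They include bleeding complications as defined above, perforation, postpolypectomy syndrome, and clinical events that require an ED visit", together with admissions, extra tests or interventions, and events during the procedure.

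**The concern.** The plan spends alpha carefully across the two looks but says nothing about alpha across the two endpoints that are to serve labelling. As written, a p-value below 0.05 on overall complications could be put forward even if delayed bleeding had failed. Because the composite adds events other than delayed bleeding, it can reach significance by chance when delayed bleeding does not.

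The stakes are narrow. Section 6 reports that the clip's indications now cover prophylactic clipping to reduce delayed bleeding. What remains exposed is a further claim on overall complications, which that indication does not cover.

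**Working it through.** **1. The plan's own figures.** For 8% vs 3%, two-sided 5% and 80% power, the usual two-proportion formula

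n = [1.96·√(2·0.055·0.945) + 0.8416·√(0.08·0.92 + 0.03·0.97)]² / 0.05² = 325.2

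gives 326 per arm. The continuity-corrected form, (n/4)·[1 + √(1 + 4/(0.05n))]² = 364.1, gives 365, which is the figure in section 3.2.10.4. So the sample size matches a continuity-corrected test, although section 3.2.10.1 does not say which chi-square will be used.

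Primary alone: critical values 2.576 (0.01) and 2.014 (0.044), correlation between looks √0.5. The bivariate normal gives an overall two-sided error of 4.89%. The primary is therefore controlled, and 5% in section 3.2.10.1 reads naturally as its overall level.

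**2. Correlation of the two tests.** Delayed bleeding (rate b) is nested in overall complications (rate o), so r = √[b(1−o) / (o(1−b))].

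- Table 1 series of polyps ≥20 mm reporting both rates: 2.9%/7.7% gives 0.60; 3.1%/5.8% gives 0.72; 5.7%/8.2% gives 0.82; 8.8%/12% gives 0.84; 10.1%/12.2% gives 0.90.
- Section 3.1.2 ("The risk of overall complications varied between 8% and 18%, with a bleeding risk between 3% and 14"%): 3%/8% gives 0.60; 14%/18% gives 0.86.
- Section 3.1.4 ("2% vs. 10%), and a reduced risk of overall complications (4% vs. 12"%): 2%/4% gives 0.70; 10%/12% gives 0.90.

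The range used is 0.6-0.9.

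**3. False favourable results under no effect.** Primary at 0.01 then 0.044; secondary at two-sided 5% at whichever analysis ends the trial; only results favouring clips are counted. Conditional power is Φ{[z√t + θ(1−t) − 2.014]/√(1−t)} with t = 0.5, and θ is either the design value 2.80 or the current trend z/√t.

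Normal model, 4,000,000 null trials per correlation:

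- Futility non-binding: primary 2.44% + lone secondary 1.91% = 4.35% at r = 0.6; 2.44% + 1.09% = 3.53% at r = 0.9. With a gate, 2.44%.
- Stop followed, design effect (51% of null trials stop): 4.08% to 3.43%, against 2.42% gated.
- Stop followed, current trend (84% stop): 3.58% to 2.67%, against 2.05% gated.

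The lone false secondary is 0.6-1.7% with the stop followed.

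**4. Binomial check.** 460 per arm, from "Therefore approximately 920 patients will need to be included"; 1,000,000 null trials. Entries are % without a gate / % with a gate. The stop-followed range covers both conditional-power bases and testing or not testing the secondary after a futility stop.

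| Bleeding / overall | Test | Non-binding | Stop followed |
|---|---|---|---|
| 3% / 8% | uncorrected | 4.2 / 2.3 | 2.7-3.9 / 1.9-2.3 |
| 8% / 12% (12% assumed) | uncorrected | 3.9 / 2.5 | 2.8-3.7 / 2.1-2.4 |
| 10% / 12% | uncorrected | 3.5 / 2.5 | 2.7-3.4 / 2.1-2.4 |
| 3% / 8% | corrected | 3.0 / 1.4 | 1.6-2.6 / 1.1-1.4 |
| 8% / 12% | corrected | 3.0 / 1.8 | 2.0-2.8 / 1.4-1.7 |
| 10% / 12% | corrected | 2.7 / 1.8 | 2.0-2.6 / 1.5-1.8 |

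Other rates within the same correlation range move the corrected figures a little: 8%/18% (r = 0.63) gives 3.3% against 1.7% non-binding.

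**5. Power cost of a gate.** Chance of a significant overall-complications result at 460 per arm, uncorrected test, futility ignored, without and then with the gate:

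- bleeding 8% vs 3%, other complications assumed in 4% of patients without bleeding: 65.2% to 64.1%;
- last row of Table 1 (bleeding 8.8% vs 3.1%, overall 12% vs 5.8%): 87.9% to 86.6%;
- section 3.1.4 rates (10% vs 2%, 12% vs 4%): 95.9% to 95.9%.

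**The case against.** The strongest reply is that the order is already implied. Delayed bleeding is the only primary endpoint, the sample size rests on it alone, and a secondary result after a failed primary is conventionally supportive. The labelling sentence does not say that either endpoint alone would suffice. If both had to succeed, the error could not exceed that of the primary. This stands as a plausible reading, but it is not written. Section 3.2.7, which calls clips effective if complications fall, can be read either way. The plan labels the cautery comparison explorative and the subgroup analyses descriptive, yet gives overall complications a formal test and a labelling purpose.

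Three further objections limit the size, and all stand. Section 3.2.10.3 says the trial will terminate for futility, so the stop-followed range is the one closer to the text. The levels depend on the form of the chi-square test. The correlation range is illustrative: Table 1 does not define its bleeding column as delayed bleeding, and the 0.60 end rests on one series, which the 3%/8% in section 3.1.2 appears to restate after rounding. If nearly all complications were bleeding, the uncorrected non-binding figure would fall to 3.3% (r = 0.95) or 2.7% (r = 1).

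A reader might infer more than the documents support:

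- *That two tests at 5% mean a 7-9% error.* That figure is two-sided, so it counts results against clips that could not support a clip label, and it needs the futility stop to be ignored. With the stop followed, the two-sided figure is 3.2-7.1%.
- *That the primary is inflated.* It is not; its overall error is 4.89%.
- *That a stand-alone claim on overall complications is planned.* The text leaves this open but does not announce it.

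**Conclusion.** The concern holds in a limited form. The plan gives no rule linking the labelling use of overall complications to the primary result. With no true effect, the probability of at least one false result favouring clips, against a one-sided benchmark of 2.5%, is:

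- uncorrected chi-square: about 2.7-4.1% (stop followed) or 3.5-4.4% (non-binding), against 1.9-2.5% with a gate;
- continuity-corrected: about 1.6-2.8% or 2.7-3.1% at the tabulated rates, against 1.1-1.8% with a gate.

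The ungated error exceeded the gated error in every case computed, but with the corrected test it can lie below 2.5% even without a gate. It would therefore be wrong to say that the plan necessarily exceeds its nominal level. The results assume that the secondary is tested at 5% at the analysis that ends the trial (or not at all after a futility stop), and rest on the illustrative rates above. A point to consider: a cheap improvement with limited consequence.

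**What to change.** In section 3.2.10.1, write:

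> Delayed bleeding is significant if p<0.01 at the interim analysis or p<0.044 at the final analysis (overall two-sided 5%). Overall complications will be tested for labelling, at two-sided 5%, only if delayed bleeding is significant in favour of clips; otherwise it will be reported descriptively with its 95% CI.

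If the intention is that both endpoints must succeed, one sentence saying so closes the same route.

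The change needs no extra patients and leaves the primary test as it is. Its cost is that overall complications can no longer support labelling on its own if the primary fails. In the examples above that is about one point of power for this endpoint.

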3.2.10.2. Secondary analysis: Entire study cohort

In secondary analysis we will further describe the rate of complete polyp resection and rate of neoplasia recurrence in all patients within 5 years, independent of their randomization. These endpoints will be calculated as proportion with 95% confidence interval. We will explore what factors might be associated with incomplete resection using logistic regression analysis.

All data collected will be summarized descriptively, overall, and by subgroups. Means will be compared using the student test if normally distributed and the Mann-Whitney test if not normally distributed.

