1. ABSTRACT

Background: The effectiveness of colonoscopy in reducing colorectal cancer mortality relies on the detection and removal of neoplastic polyps. Because the risk of prevalent cancer and of transition to cancer increases with polyp size, effective and safe resection of large polyps is particularly important. Large polyps $\geq 20\text{mm}$ are removed by so-called endoscopic mucosal resection (EMR) using electrocautery snares. Resection of these large polyps is associated with a risk of severe complications that may require hospitalization and additional interventions. The most common risk is delayed bleeding which is observed in approximately 2-9% of patients. A recent retrospective study suggests that closure of the large mucosal defect after resection may decrease the risk of delayed bleeding. However, significant uncertainty remains about the polypectomy techniques to optimizing resection and minimizing risk. Important aspects that may affect risk include clipping of the mucosal defect and electrocautery setting.

Aims/Hypothesis: Our primary aim is to examine whether clip closure of the mucosal defect after endoscopic mucosal resection (EMR) of large polyps ($\geq 20\text{mm}$) will reduce the risk of delayed bleeding in a prospective randomized trial. In secondary analysis we will explore, whether electrocautery settings affect the risk of complications. We hypothesize that clip closure will reduce the risk of delayed bleeding.

Methods: The study will include patients with a polyp $\geq 20\text{ mm}$ in size. Experienced endoscopists will follow a standardized resection protocol. Patients will be randomized in a 2×2 factorial design to one of two electrocautery settings (Endocut versus low power coagulation; secondary comparison) and to either undergo or not undergo closing of the mucosal resection defect after resection. For the primary comparison (clip vs. no clip) the primary outcome will be incidence of delayed bleeding complications within 30 days following the procedure. We further plan to identify factors that may be associated with delayed bleeding. We are also interested in understanding recurrence of neoplastic polyps at first and second follow-up colonoscopy, defined as the presence of biopsy proven neoplastic tissue.

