3.2.5. Allocation to treatment (Randomization process)

Randomized will occur at the time of colonoscopy when a polyp has been identified as a study polyp using computer generated randomization. Patients will be randomized following a 2 x 2 factorial design to: (i) Endocut vs. low power coagulation after inspection of the polyp and decision to resect the polyp, and (i) clipping vs. no clipping of the mucosal defect after resection.

Patients will hence be randomized to one of four groups:

- A) Endocut and clipping,
- B) Endocut and no clipping,
- C) Low power coagulation and clipping, and
- D) Low power coagulation and no clipping.

Should a patient have more than one study polyp, all polyps will be resected in the same way (per patient randomization). The primary comparison will be between clip and no clip application. The comparison between cautery currents is secondary and exploratory.

Breaking the blind: The study is not blinded.

Treatment adherence/study compliance: The primary intervention (one-time clip placement) does not require adherence to the intervention. Participants will therefore not be excluded because of non-compliance.

The major outcome of interest will be assessed after 30 days following the intervention by a phone call. We expect that such short interval will allow an almost complete follow-up.

Secondary outcomes of interests include polyp recurrence during longer-term follow-up. We will collect data on all follow-up procedures that are performed as per standard of care (not as a study intervention).

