3.2.9.1. Outcome measures

Primary Outcome Measure:

- Delayed bleeding complications [Time Frame: 30 days].

Assessment: Patient contact, if severe adverse event, review of medical records, to obtain details on complication, treatment and outcome.

Secondary Outcome Measures:

- Overall complications [Time Frame: 30 days]
Assessment: Patient contact, if severe adverse event, review of medical records, to obtain details on complication, treatment and outcome.
- Factors associated with complications [Time Frame: 30 days].
Assessment: Using patient and polyp characteristics, and procedural data, obtained at the time of study polyp resection.
- Complete polyp resection [Time Frame: 6 months]
Assessment: a) immediately after polyp resection, based on evaluation of the endoscopist. b) at first follow-up endoscopy, based on results of biopsies from the resection site.
- Polyp recurrence [Time Frame: 3 months to 5 years].
Assessment: at follow-up endoscopies after complete resection was achieved.
- Factors associated with incomplete resection or recurrence [Time Frame: 5 years].
Assessment: Using patient and polyp characteristics, and procedural data, obtained at the time of study polyp resection.

Procedures to assess safety of clip use

- Clip complications [Time Frame: 30 days].
Assessment: Patient contact, if severe adverse event, review of medical records, to obtain details on complication, treatment and outcome.

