5. RISK ANALYSIS

5.1. Anticipated Risks

There are no risks incurred with the study that are beyond those associated with the clinically warranted procedure (colonoscopy with EMR, see background section). In theory there is a minimal risk associated with an increased time needed to apply clips for closure of the mucosal defect. Dependent on the size of the lesion endoscopic clipping may take 5 to 10 additional minutes. Considering that an EMR of large polyps often takes more than 60 minutes, the additional relative increase in procedure time would be low. Furthermore, there has been no study to show that a small proportional increase in procedure time is associated with an increased risk. Should there be any concern regarding the safety of the patient related to prolonged procedure time when applying clips, the procedure will be aborted.

Risk/Benefit analysis. It is unknown whether the patient will benefit from the proposed study.

The planned interventions are variations of standard of care and the study compares different approaches representing a comparative effectiveness study. While the risk of added time in the clip group may be minimal (if present at all), it is plausible that clip application will decrease bleeding risk and may improve polyp resection. If so, fewer follow-up procedures (either colonoscopy or surgery) would be needed, which might lower the future overall risk. Whether clip application is truly a helpful modification of the EMR resection practice is not known, hence the study.

As for the comparison of cautery settings (Endocut vs. lower power coagulation), it is unclear, which mode is associated with fewer complications. It is the purpose of this study to explore whether one choice of cautery setting may be associated with a lower risk. This understanding may ultimately contribute to an improved polyp resection practice.

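### Five-year recurrence is planned as a simple pooled proportion with no rule for incomplete follow-up, and no estimate by clip arm is planned for resection or recurrence

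*Combined protocol and SAP*

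**What the plan says.** Section 3.2.10.2 covers complete resection and recurrence for the entire cohort. It will describe the "rate of neoplasia recurrence in all patients within 5 years, independent of their randomization", and adds: "These endpoints will be calculated as proportion with 95% confidence interval". The only model named there is exploratory: "We will explore what factors might be associated with incomplete resection using logistic regression analysis". A general sentence follows: "All data collected will be summarized descriptively, overall, and by subgroups".

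Other sections bear on this:

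- **Source of the exams.** Section 3.2.5 takes long-term data from routine care: "We will collect data on all follow-up procedures that are performed as per standard of care (not as a study intervention". Section 3.2.7 aims for exams at 3 to 4 months and one year after that. Later exams depend on findings, the third typically three years after the second. Section 5.3 ends follow-up at withdrawal.
- **Definitions.** Section 3.2.9.1 assesses complete resection twice: by the endoscopist immediately after resection, and "b) at first follow-up endoscopy, based on results of biopsies from the resection site". Recurrence is assessed once complete resection has been achieved, with a window opening at 3 months. Section 3.2.9.2 also restricts recurrence to completely resected sites. The abstract speaks of "recurrence of neoplastic polyps at first and second follow-up colonoscopy, defined as the presence of biopsy proven neoplastic tissue".
- **Arms.** The between-arm tests in Section 3.2.10.1 cover delayed bleeding and overall complications only. Section 5.1 says "it is plausible that clip application will decrease bleeding risk and may improve polyp resection".

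**The concern.** Recurrence during 5 years of follow-up is a stated secondary aim (Section 2). A simple proportion estimates 5-year recurrence only if every patient in the denominator is observed for the whole period. Here the exams are not under the study's control and their number and timing differ between patients. On the schedule in Section 3.2.7 the third exam falls at about 51 to 52 months (3 to 4, plus 12, plus 36). A cumulative delay of 8 to 9 months therefore puts it outside the 5-year window. No section gives a rule for missed exams, withdrawal, surgery or death. The statement in Section 3.2.10.4 that no dropouts are expected refers to the 30-day outcome.

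Two things are at stake. The reported percentage and its interval could be off in a direction that depends on a denominator the plan does not settle. And a randomised comparison of residual and recurrent neoplasia, available from data already being collected, would not be prespecified.

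**Working it through.** The plan gives no expected recurrence rate, retention or precision for recurrence, so there is no figure of its own to reproduce. The only design input used below is the 920 patients expected to undergo the intervention (Section 3.2.10.4), or 460 per arm.

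**1. Recurrence after a clear first follow-up exam.** All rates here are assumptions. 5% of still-clear patients are positive at exam two and 5% at exam three; 75% attend exam two, and 55% of those still followed attend exam three; loss is unrelated to outcome.

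- True cumulative recurrence: 1 − 0.95 × 0.95 = 9.75%.
- Events seen at exam two: 0.75 × 0.05 = 0.0375.
- Still clear and seen at exam three: 0.75 × 0.95 × 0.55 = 0.3919. Events there: 0.3919 × 0.05 = 0.0196.
- Events seen in total: 0.0375 + 0.0196 = 0.0571.

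| Denominator | Calculation | Result |
|---|---|---|
| All patients clear at the first exam | 0.0571 / 1 | 5.7% |
| Those with at least one later exam | 0.0571 / 0.75 | 7.6% |
| Event, or event-free at exam three | 0.0571 / (0.0571 + 0.3919 × 0.95) | 13.3% |
| Life table | 1 − (1 − 0.0375/0.75)(1 − 0.0196/0.3919) | 9.75% |

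**2. The same check with other inputs, counting from the index resection.** Assume a true 5-year rate of 16% (the lower end of the background range for residual neoplasia in Section 3.1, used only as an illustration), with events split 50/30/20 over three exams.

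- Retention 80/60/40%: events seen = 0.16 × (0.5 × 0.8 + 0.3 × 0.6 + 0.2 × 0.4) = 0.1056. Over all patients this is 10.6%. Over those examined at least once it is 0.1056/0.8 = 13.2%. Over events plus complete event-free follow-up it is 0.1056/(0.1056 + 0.84 × 0.4) = 23.9%.
- Retention 90/80/70%: the same three figures are 13.3%, 14.8% and 18.4%.
- Full retention: all three equal 16%. The life table gives 16% in each case.

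**3. Definitions side by side.** Section 3.2.10.2 refers to all patients; Section 3.2.9.2 refers to completely resected sites. If completeness is the endoscopist's judgement at the index exam, a positive biopsy at the first follow-up shows incomplete resection under Section 3.2.9.1. It also falls inside the recurrence window, and the abstract counts it as recurrence. If completeness is judged at the first follow-up, the overlap disappears. The plan does not say which applies.

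**4. Precision of a by-arm difference at the first follow-up.** Half-width = 1.96 × √(2 × 0.15 × 0.85 / n), assuming 15% in each arm. With n = 460 this is 4.6 points. With n = 390 (about 85% of 460) it is 5.0 points. For a given proportion it widens at later exams as fewer patients are seen.

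**The case against.** The strongest reply is that these endpoints are descriptive, that neither the primary test nor the endpoints meant to support labelling are touched, and that the plan does not commit to the worst reading. Much of this stands.

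- A reader might infer that unexamined patients are counted as recurrence-free, so that recurrence is certain to be understated. No section says so. The reference to all patients can mean simply that both arms are pooled. Sections 3.2.9.1 and 3.2.9.2 tie recurrence to follow-up exams after complete resection, and the abstract's wording would also allow visit-specific proportions among those examined. Better attendance by patients with residual polyp would push the figure up.
- A reader might infer that the plan counts one event in two endpoints. The outcome section mostly prevents this by requiring complete resection first; what remains is the ambiguity about when completeness is judged.
- A reader might take Section 5.1 as a hypothesis left untested. It calls a resection benefit plausible within a risk/benefit paragraph and says the value of clipping is not known. It is not an aim. Summaries by subgroup (Section 3.2.10.2) and the use of procedural data as factors (Section 3.2.9.1) leave room for an exploratory look at clipping.
- Kaplan-Meier is not a complete cure, because findings-driven exams may make censoring informative.

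What does not fall is that the stated estimator takes no account of unequal follow-up, the denominator is not settled, and no by-arm estimate is prespecified.

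**Conclusion.** The point holds as a defect of method in a secondary aim and should be corrected. With incomplete follow-up, the planned proportion is biased downward if all patients, or all with at least one exam, form the denominator, and upward if only patients with an event or complete follow-up do. On the assumed attendance, a true 9.75% becomes 5.7%, 7.6% or 13.3%. These sizes rest on assumed positivity and attendance and on loss unrelated to outcome; the documents supply none of these.

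A larger-looking gap comes from adding first-exam positives. With 15% positive at an exam that 85% attend, the true figure becomes 1 − 0.85 × 0.95 × 0.95 = 23.3%, and the crude one 0.1275 + 0.0271 + 0.0142 = 16.9%. That should not be used as the size of the problem, because it mixes residual neoplasia with recurrence after complete resection.

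The missing by-arm estimate is an omitted opportunity in a randomised trial. It does not contradict a stated objective.

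**What to change.** In Sections 3.2.9.2 and 3.2.10.2:

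1. Count neoplasia at the first follow-up once, as residual or incomplete resection.
2. Define recurrence among patients clear at that exam and start the clock there.
3. Estimate recurrence by a life-table or interval-censored cumulative incidence from actual exam dates, with the number examined at each stage. State whether surgery and death are competing or censoring events, and note that findings-driven exam timing may make censoring informative.
4. Report both endpoints pooled and, labelled exploratory, by randomised clip arm with a difference and 95% CI. Recurrence among patients clear at the first exam is a post-randomisation subset, which is a further reason for the label.

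The cost is SAP wording and modest extra analysis, with no new visits or patients. Procedure and surgery dates are already to go to the coordinating centre, subject to consent (Section 7); death is not named among them and may need adding. The downsides are a less simple estimate that relies on a censoring assumption, and a by-arm comparison of limited precision: about ±4.6 to 5.0 points at the first follow-up, and wider later for the same proportion.
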